9.5. Interim analysis

There is no planned interim analysis in this investigation..

9.6. Statistical reason for termination of investigation

There will be no interim analysis and therefore no reason to terminate the investigation based on statistical considerations.

9.7. Deviation(s) from statistical design, method or analytical procedures

Any deviations from the statistical plan will be documented in the clinical investigation report.

10. Data management

10.1. Data Collection in the clinical investigation

Data management and the final statistical analyses of all measurements described in this protocol are carried out by the Medical Affairs, Coloplast A/S.

Data will be collected through an electronic data capturing (EDC) system on electronic Case Report Form (eCRF), a secure, internet-based case report form. This system will be used to record all subject information collected in the investigation for secure data tracking and centralised data monitoring ("remote monitoring") done by monitors, as defined in the monitoring plan.

The EDC system used is [REDACTED] The system is designed to be compliant with the FDA requirements of 21 CFR part 11. It is a validated data management system allowing only qualified and trained personnel to enter the system. The system has full audit trail and electronic signature.

The sponsor will be responsible for training the investigator, or delegate, in completion of the eCRF.

Principal Investigator, or delegate, at the clinical site will perform primary data collection directly into the eCRF or drawn from source-document (medical records) reviews. The eCRF will be completed on a continuous basis starting from the point of enrolling the subject to final follow up.

The eCRF will be completed by the investigator, or delegate, who have signed the Site Personnel Signature and Delegation List and Clinical Investigation Training Log. It will be the responsibility of the investigator to ensure that all measurements and observations are correctly noted in the eCRF.

All assessments and observations throughout the investigation for each subject must be carefully recorded in an eCRF or in a paper CRF (pCRF) during the visit or immediately after. The eCRF makes it possible to enter data right away when they are obtained. This is the preferred way of collecting data. In case this is not possible the data should be entered no later than 7 days after the visit / procedure.

Adverse events should be registered following the timelines described in the Adverse Event section.

When subject and investigator is required to complete different sections in the CRF, it will be specified which sections the subject will fill in and which sections the investigator will fill in. Please see the flow chart section 7.3 for details.

Additional data from other apps or external companies will be batch loaded into the EDC system.

In the unforeseen situation, where site cannot establish connection to the EDC system a paper CRF (pCRF) has been printed and supplied by sponsor.

The investigator will keep a separate list of the subjects' ID numbers, names and addresses in a locked room/cabinet. Only data referred to in this clinical investigation plan will be recorded in the CRFs.

10.2. Database Management, Queries and Quality Control

The data management system has restricted role-based access control. The principal investigator or delegate must be trained in the system prior to getting access. The training is web-based and must be completed before access to the investigation is granted. Training will be documented in the data management system. Only the principal investigator, or delegate, will be authorised to enter data in the eCRF.

The monitor, using his/her personal login information shall verify all critical data points against the source documents and issue electronic queries for the authorised clinical site personnel to respond, as defined in the monitoring plan.

CONFIDENTIAL

Page 27 of 34

The principal investigator, using his/her personal login information shall sign each eCRF.

Automated, real time access to the data enable control on study compliance and safety assessments.

A critical quality control will be performed by the sponsor's data management team and queries issued where needed. Such queries will be reviewed by the monitor and must be resolved by the site personnel.

At the end of the study a formal data review meeting will be performed before the database will be locked.

A full audit trail ensures, that each user's (site personnel, monitor, sponsor, data manager) access to and actions in the system is tracked.

The Data Management Procedures are further described in the Data Management SOP's.

10.3. Data retention

The sponsor file will be archived for a minimum period of 10 years after the final clinical investigation report has been signed.

All investigation site documents will be archived for a minimum period of 10 years after the final clinical investigation report has been signed.

11. Amendments to the CIP

Any significant changes to the CIP are:

- Agreed between sponsor and PI
- Justified in a statement included in the amended section and the version number and date of amendment must be documented
- Registered in the Change Log
- Notified to or approved by the EC before implementation
- Notified to or approved by the regulatory authorities before implementation

Example of significant change: Changes of inclusion criteria, end points or assessment methods.

12. Deviations from Clinical Investigation Plan

The Investigator is not allowed to deviate from the CIP unless under emergency circumstances and to protect the rights, safety and well-being of the subject(s). Deviations must be reported to sponsor and deviations affecting the scientific aspect of the investigation or the safety of the subject are reported to the EC by sponsor if required.

In case of continued or repeated deviations affecting the scientific aspect of the investigation or the subjects' rights, safety and well-being sponsor will disqualify the Investigator from further participation in the investigation.

13. Device Accountability

All access to the investigational devices used in the clinical investigation is controlled by storage procedures and device accountability logs as described below. The investigational devices must only be used in this clinical investigation and only per this CIP.

Sponsor keeps a device accountability log that states the physical location of all investigational devices from shipment of investigations devices to the investigational sites until return of or disposal.

The Investigator or an authorized designee keeps records documenting the receipt, use and return and disposal of the investigational devices, which includes:

- Date of receipt
- Identification of each investigational device (batch no./serial no./unique code) and number received
- Number of devices used
- Subject identification
- Identification of each investigational device (batch no./serial no./unique code) and number returned
- Date of returned investigational device

14. Statement of compliance

The clinical investigation is conducted in accordance to:

- Ethical principles that have their origin in the Declaration of Helsinki, 1964, Last amended at the 59th WMA General Assembly, Brazil, October 2013.
- MDD 93/42/EEC as amended by Directive 2007/47/EC (commonly known as the Medical Device Directive).
- MDR 2017/45.
- GDPR: Regulation (EU) 2016/679 of the European Parliament and of the Council of 27 April 2016 on the protection of natural persons with regard to the processing of personal data and on the free movement of such data, and repealing Directive 95/46/EC (General Data Protection Regulation).
- ISO 14155:2011 "Clinical Investigation of medical devices for human subjects – Good clinical practices".
- Any applicable regional or national regulations will be specified in the country specific CIP.

14.1. Ethics committee and regulatory authorities

The investigational device will be CE-marked prior to study start and used per IFU. The CIP and/or other relevant documents are submitted to the appropriate EC(s). This clinical investigation will not begin until the required approval from the EC has been obtained. Any amendment to the protocol will be submitted to the same EC(s).

Sponsor will notify the relevant EC(s) concerned of the end of the clinical investigation.

14.2. Data protection

All personal data are kept as long as required by applicable laws and regulations. The EU Medical Device Regulation obliges Coloplast to retain data for a period of at least ten years after the end of testing, or in the event that the product is subsequently marketed, for at least ten years after the last product has been placed on the market. All personal information will be deleted at the end of the mandatory retention period. Data will be stored by the vendor of the data management system Medidata Solutions in the US.

Each subject is entitled to get access to all the data and to have rectified any inaccurate data Coloplast is processing about the subject. All data are collected based on the consent each subject has given when being eligible and enrolled in the investigation. The subject is entitled to withdraw the consent at any time, and Coloplast will then cease to use such personal information for further innovation and improvement of products. The already data collected and handled in the investigation will not be retired.

The subject will be requested to check www.coloplast.com/global/privacy-notice for further information about the Coloplast's Global Privacy Notice. This will be described in the Subject Information Form/informed Consent Form.

CONFIDENTIAL

Page 29 of 34

All information collected during this investigation is kept strictly confidential. Subjects are identified by an investigation number and the investigation monitor has limited access to subjects' notes/documentation for source data verification. Any information which could identify a subject remains with the investigator where it is archived with investigation documents. Subjects remain anonymous for data analysis. If payment to a subject's bank account is needed (e.g. transportation reimbursement) it may be necessary to collect subjects' social security number, which will then be confidentially handled.

Should the investigation require future review, relevant regulatory authorities and ethics committees will be allowed access to all relevant information for audit and inspection purposes.

Information collected at interviews will be archived confidentially and safe, as all other collected data in this investigation. User Insight works with the usability of the developing Coloplast products, and all collected data from interviews will in general be used in the product development at Coloplast A/S. The collected data will at that time be taken out of the specific relevant interview and context, and the subject, who has participated with this kind of data, is not able to identify.

14.3. Indemnity

14.4. Financial conditions

Coloplast A/S has taken the initiative to this study and Coloplast A/S will compensate all investigators involved in the clinical investigation for their time and resources spent on the investigation. The expenses include the salary to the Principal Investigator and study nurses, the cost of test products, shipments, transportation and gift certificates. The Principal Investigator and study nurses have no financial interest in the investigation. The total budget for the investigation is [REDACTED] covering 20 participants, each participating in 2 test visits. The expenses are paid on an ongoing basis. All financial agreements with the investigation sites involved in the clinical investigation will be specified in a sponsor investigator Agreement.

Subjects will be paid for their participation in the study and receives a gift voucher equivalent in value to [REDACTED] if the subject completes the investigation. If interviews will be conducted, subjects will be paid for their participation in the interview and receives a gift voucher equivalent in value to [REDACTED] interview, in [REDACTED] if the subject completes two interviews.

15. Informed consent process

Written informed consent is obtained from all subjects participating in the investigation after thorough written and verbal information. The information is given by the investigator or his/her representative in the subjects' native non-technical language. Each subject will be fully informed about the aim of the investigation, procedures, potential risks or inconveniences and/or expected benefits and have a minimum of 24h before deciding on participation. The subjects will be informed that their participation is voluntary and that they may leave the investigation at any time, without this having any influence on their further treatment.

The informed consent signature form includes personally dated signatures of the subject and the PI or his/hers representative responsible for conducting the informed consent process. A copy will be provided to the subject.

If new information is to be given during the investigation, sponsor will inform the investigators, and the new information is given to the subjects by the investigator. If new information becomes available that can significantly affect a subject's future health and medical care that information will be provided to the subject in written form. The Coloplast CM is responsible for writing the information and providing it to investigators that will further provide it to the subjects. If applicable, all affected subjects shall be asked to confirm their continuing informed consent in writing.

This procedure also applies to informed consent obtained from a subject's legal representative. The procedure cannot waive the subjects' legal rights.

16. Adverse events, adverse device effects and device deficiencies

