6.3. Subject withdrawal criteria

The subject can withdraw from the investigation at any time for whatever reason without any consequences for their future treatment outside the clinical investigation. Investigator may withdraw a subject from the investigation at any time if they judge it to be the subject's interest.

The investigator must withdraw a subject from the investigation due to:

- Non-compliance with the CIP impacting the scientific integrity of the investigation
- If subject's safety and wellbeing is compromised by further participation.

Withdrawn subjects will not be replaced by new subjects.

A subject who is withdrawn from the investigation, for any reason, will be encouraged to contact the investigator if problems arise that the subject believes are related to the clinical investigation. Subjects who have not experienced any adverse events will not be followed up. For subjects who experience adverse events, see section 16.

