7.1.1. Visits

Visit 0 (Inclusion visit)

If a potential subject is interested in participating after the first contact, a visit (visit 0) will be arranged at subject's home or at a clinic or at Coloplast, if subjects prefer not to have visits in own home, in a room reserved to ensure privacy and quiet surroundings. When arranging the visit, it will be ensured, that the subject has received the Subject Information Form prior to the visit. The subjects will receive both written and verbal information to ensure that the subject understands what was read and explained and can freely agree to participate in the investigation. The subject will, beforehand, also be informed about the possibility of bringing a companion to Visit 0 and to any possible subsequent visits. During the visit the principal Investigator, or delegate, will provide oral information about the investigation based on the Subject Information Form. The subject has the right to wait before deciding on participation.

If/when subjects decide to participate, they will be asked to sign the Informed Consent Signature Form. If a subject so desires, and it is certain that it is understood what the investigation entails, and the relevant form has been signed, the subjects are considered enrolled in the investigation. Enrolled subjects that are deemed eligible per the inclusion/exclusion criteria are allocated a subject number. Visit 0 and visit 1 can be combined.

Visits 1 (V1)

During visit 1, part 1 of the questionnaire Table 1 (demographic questions) will be completed by the Principal Investigator, or delegate. The subject will be trained in the use of the test product per IFU. The subjects are instructed to continue their everyday life and change test product whenever they feel the need to.

Visits 2 (V2)

During visit 2, the Principal Investigator, or delegate will ensure part 2 of the questionnaire [Table 2](#) will be completed by subjects. Potential (S)AE's will be captured by the Principal Investigator, or delegate. Hereafter termination If appropriate, subjects may be interviewed regarding use of the test product by a Coloplast representative at V2, otherwise an alternative time for interview may be scheduled.

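### The voucher depends on completing the investigation, with no payment rule for a man who leaves early, so men who exit before V2 may go unpaid and their answers may be missing from every claim

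*Combined protocol and SAP*

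**What the plan says.** **Payment (section 14.4).** The opening words are general: "Subjects will be paid for their participation in the study and receives a gift voucher". The same sentence then attaches the condition: "gift voucher equivalent in value to [REDACTED] if the subject completes the investigation". The amount is blacked out, which does not matter here because the condition itself is legible. The section does not define completion, offers no part-payment, and does not say what a man receives if he withdraws or is withdrawn. Interviews carry a separate voucher.

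**Withdrawal (section 6.3).** A man may leave at any time "without any consequences for their future treatment outside the clinical investigation". That assurance covers treatment and does not mention payment. The section goes on: "The investigator must withdraw a subject from the investigation due to" either of two grounds, each with a qualifier. The first is "Non-compliance with the CIP impacting the scientific integrity of the investigation". The second is "If subject's safety and wellbeing is compromised by further participation". Withdrawn men are not replaced, and those without adverse events are not followed up.

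**Data collection (sections 7.1.1 and 7.3).** At V2 the "Principal Investigator, or delegate will ensure part 2 of the questionnaire" is completed. Section 7.1.1 also places the capture of adverse events and termination at that visit. Table 1 has only two visit columns, V0/V1 and V2, and Part 2 is marked at V2 alone. On wear, "The subjects are instructed to continue their everyday life and change test product whenever they feel the need to"; no minimum wear is set.

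**Analysis (sections 9.1 and 9.4).** The ITT set requires valid consent, exposure to at least one product and at least one non-missing endpoint. A claim is supported when the lower 95% confidence limit for the success proportion exceeds 50%.

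**The concern.** Three provisions that are ordinary on their own combine badly. The voucher depends on completing, some withdrawals are mandatory, and all endpoint data come from one self-report at the last visit.

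On an ordinary reading, a man withdrawn before V2 has not completed. He cannot tell from section 14.4 whether he will be paid, and neither can the site. Two consequences follow:

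- **Lost answers.** A man who leaves early has no payment reason to answer Part 2, and no early occasion to answer it is scheduled. Without a recorded endpoint he is outside the ITT set, and so outside the denominator of every claim. If men who leave early tend to be those the product suited least, the remaining proportions are too favourable.
- **Delayed reports.** No contact is scheduled between V1 and V2, so a report of a problem in that interval depends on the man's own initiative. A completion condition gives him some reason to wait.

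The claims are commercial and rest on about 20 men, so a few missing answers could decide whether a claim is supported.

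**Working it through.** The plan gives no figure on this point to reproduce: no early-exit rate, no sample size calculation and no power. The check is a reading of the text, followed by arithmetic for scale.

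**Step 1. Follow a man who leaves before V2.**
- Payment: conditional on completion and silent on his case (14.4).
- Part 2: scheduled only at V2 (Table 1), so by default he gives no endpoint data.
- Analysis: no recorded endpoint means he is not in the ITT set (9.1).
- Replacement: none (6.3), so the denominator falls by one.

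**Step 2. Follow a man who stops wearing the product but attends V2.**
- No minimum wear is set (7.1.1), so stopping is not shown to be non-compliance.
- He answers Part 2, counts in the ITT set because he used at least one product, and may rate the product as badly as he likes.
- If completing means attending V2, he is paid.

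The problem therefore lies with exit before V2, and with reports made between V1 and V2.

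**Step 3. How many lost answers would matter.** Inputs: 20 men (section 6), two-sided alpha of 0.05 and an exact binomial analysis (9.1), and the pass rule (9.4). The exact (Clopper-Pearson) lower limit for x successes in n is the 0.025 quantile of a Beta(x, n − x + 1) distribution. It exceeds 50% exactly when P(X ≥ x | n, 0.5) is below 0.025.

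| Successes / n | Lower 95% limit | Result |
|---|---|---|
| 15/20 | 50.9% | pass |
| 14/20 | 45.7% | fail |
| 14/19 | 48.8% | fail |
| 14/18 | 52.4% | pass |
| 13/20 | 40.8% | fail |
| 13/17 | 50.1% | pass |

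Tail check by counting outcomes:
- 14/20: (38760 + 15504 + 4845 + 1140 + 190 + 20 + 1)/1048576 = 60460/1048576 = 0.058, above 0.025.
- 14/18: (3060 + 816 + 153 + 18 + 1)/262144 = 4048/262144 = 0.015, below 0.025.

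Starting from 14/20, the loss of one dissatisfied man leaves the claim failing (14/19) and the loss of two makes it pass (14/18). Starting from 13/20, the loss of three is enough (13/17). The reverse also holds: from 15/20, the loss of one satisfied man gives 14/19 and a failed claim. The bias favours the product only if leavers are mainly dissatisfied. That is plausible for men who leave over a product problem, but the documents give no data on it.

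**The case against.** The strongest reply is that completion most naturally means attending V2, because Part 2, adverse-event capture and termination all take place there. On that reading the voucher gives a dissatisfied man a reason to return. His poor ratings then stay in the denominator and count against a claim. Section 14.4 also speaks of payment for participation, and the Subject Information Form, which is not available here, may hold a part-payment rule. Much of this stands. It does not help the man who withdraws or is withdrawn before V2, because section 14.4 still does not say whether he is paid and Table 1 schedules no Part 2 for him.

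A reader might infer something stronger: that section 6.3 forces withdrawal for any non-compliance or any problem, so that admitting non-use or skin irritation costs a man the voucher. The documents do not support this. Both grounds are qualified, no minimum wear makes stopping a breach, and intact-skin irritation is an anticipated effect in Table 3 (3-25%) that nothing makes an automatic withdrawal ground.

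Nor do the documents support saying that every effect of the voucher favours the product, or that one man's concealed non-use changes a claim. Payment does not depend on the answers, and hiding non-use does not turn a discomfort rating into a success. A man who stays silent and attends V2 remains in the analysis.

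The safety effect is also limited. The test period is one week plus up to three days, adverse events are captured at V2 in any case, and withdrawn men are encouraged to make contact if problems arise.

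**Conclusion.** The point holds as a gap in the payment rule that meets a single end-of-study assessment. It is neither a contradiction nor a numerical error. Section 14.4 states a completion condition without defining it and without covering men who leave. Because Part 2 exists only at V2 and the ITT set needs a recorded endpoint, a man who leaves earlier may be unpaid and, by default, is absent from every claim. The condition may also discourage reporting between V1 and V2.

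The size of the effect is unknown. The documents give no rate of early exit or delayed reporting, and the voucher's value is not visible. The figures show only that at n = 20 the loss of two dissatisfied men can turn a failed claim (14/20, 45.7%) into a supported one (14/18, 52.4%). That fragility belongs to the sample size and would apply to any cause of loss.

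The conclusion assumes that a man withdrawn before V2 does not count as having completed, and that no other document fills the gap. The change is worth making because it is cheap and protects the answers most likely to be unfavourable.

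**What to change.** In section 14.4 and the Subject Information Form, state that every man who received the product is paid the study voucher if he answers Part 2 and the adverse-event questions, at V2 or at an earlier exit contact. Say that this applies whether or not he kept wearing the product, and includes men withdrawn under section 6.3. In Table 1, allow Part 2 and the termination form at early exit.

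The ITT definition needs no change: a man who used at least one product and answers at exit already qualifies.

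The cost is a few extra vouchers, an early questionnaire for the few men who exit, and an amendment handled under section 11. Ratings given at exit will reflect less than the full week of use, so the report should identify them. No withdrawal criterion changes.
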